Finally, the costs associated with the use of MS DMTs have skyrocketed over the 21+ years since the original approval of interferon β-1b in 1993. Based on 2013 prices, the average cost of both the newer and older DMTs is about \$60,000 per year.⁵⁵ This does not include costs related to medical office visits for monitoring, the monitoring costs themselves (e.g. laboratory studies), lost time at work, infusion costs (for natalizumab, alemtuzumab and mitoxantrone), or the extra costs incurred when drug-related side effects develop and need to be managed with other interventions (e.g. treating infections). Seven of the 80 most costly drugs in the US in 2014 were MS DMTs,⁵⁶ accounting for expenditures over \$11 billion. At \$60,000 per year, 100 patients aged 55 would collectively spend \$60,000,000 if they continued to use a MS DMT over a decade until age 65. While medical insurance has covered a great deal of the financial burden, representing a large societal burden, many of these costs are borne by the patient and their family as well. Of course, if the medications are beneficial, and result in costs savings due to less disability and related issues (e.g. unemployment due to MS), these costs may be justifiable. The use of simulation models and outcome measures such as the quality-adjusted life year has allowed for cost-effectiveness comparisons between the various DMTs⁵⁷. But if at some point and/or some age there is minimal benefit, or an overall detrimental effect on neurological/other function with continuation of MS DMTs, it would be difficult to justify their ongoing use.

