The patient viewpoint is central to decision-making when considering discontinuation of a MS DMT, and might be based on a variety of factors that have more to do with daily symptoms and quality of life, and less to do with potential and theoretical long-term benefits, such as less new relapses and brain MRI lesions. Important symptoms will be assessed with the PROs we have chosen so far. We will also assess the potential role of side effects in decision-making, comparing these at baseline and over time. Our study design will allow us to compare a series of patient-centered outcomes focused on a broad array of symptoms and functions in those discontinuing vs continuing MS DMTs. While many MS patients recognize the importance of the relapse, EDSS and MRI activity, it will also be extremely important to ascertain the relative levels of importance of these physician-derived measures compared to the PROs. That is, it is possible study participants will accept trade-offs that favor one outcome or set of outcomes compared to another. For example, a patient may be willing to accept a small change on a brain MRI scan, if they no longer have side effects of a DMT, or have significantly increased disposable income due to elimination of drug and related costs. The patients themselves will be indispensable in trying to understand how these trade-offs might be contemplated and acted upon.

This is a pragmatic clinical trial, based on real world patterns of patient decision-making. As such, all of the study visits will be attached to routine office visits, and the patient/their insurance will be responsible for payment of standard

of care aspects related to the study. This will include a baseline brain MRI, as well as annual brain MRI scans at year one and year two, and all routine safety monitoring as would be obtained in a typical office setting for that individual medication. The funding agency, the Patient Centered Outcome Research Institute (PCORI), will be responsible for all research aspects, including data acquisition and manipulation, performance of a 6-month “safety” brain MRI (which is NOT standard of care), all research personnel, and all regulatory review. In addition, while this is a randomized discontinuation trial, all patients will be aware of their medication assignment, but observers of the main outcomes (relapses, MRI changes and the EDSS) will be blinded.

III. Research Methods

A. Outcome Measure(s):

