Comorbidities	X	X	X	X	X	X	
Neuro-QoL Short Form	X	-	-	****	X	X	
PDSS	X	X	X	X	X	X	
SymptoMScreen	X	X	X	X	X	X	
MSIS-29	X	X	X	X	X	X	
SDMT	X	X	X	X	X	X	
Treatment Satisfaction Question	X	X	X	X	X	X	
Relapse Assessment	X	X	X	X	X	X	
EDSS (by unbiased Rater)	X	X	X	X	X	X	
Treatment Decision Questions	-	-	-	****	X	X	
MRI**	X	X	X	****	X	-	

*Unscheduled visits may occur for patients during the study. If an MRI is requested by the PI in relation to an unscheduled visit, that MRI would be paid through standard of care.

**T₀, T₂, and T₄ MRIs paid as part of standard of care (SOC). T₁ MRI paid as research only and must be performed at the study site. T₀ Brain MRI to be performed within 6 months preceding study entry, and will be reviewed and confirmed as fulfilling entry criteria. If T₀ MRI results for a potential subject from within the last 6 months are not available, the patient should be scheduled for a Standard of Care MRI and these results should be reviewed for inclusion/exclusion criteria prior to enrollment into the study and completion of Baseline visit.

***Participants enrolled after July 31, 2019 may not complete T₄, but will be followed until September 1, 2021. If T₃ is on or before June 30, 2021, participant should come in for an out of window T₄ visit before Sept. 1, 2021.

****If T₃ falls after June 30, 2021, participants will not come in for a T₄ visit, but will complete a NeuroQoL and Treatment Decision Question during T₃, and will have an out of window Month 24 MRI.

After thorough discussion of the trial and signing an informed consent, participants will be seen at five specified time points: T₀, screen/baseline; T₁ at 6 months; T₂ at 12 months; T₃ at 18 months; and T₄ at 24 months. Patients will be screened, have a baseline brain MRI reviewed, undergo a relapse assessment and EDSS exam, complete all PROs, and be randomized at T₀. They will be examined every 6 months at times T₀, T₁, T₂, T₃, and T₄ and undergo MRI scans of the brain at times T₀, T₁, T₂, and T₄. If T₃ occurs after June 30, 2021, participants will not be seen for a T₄ visit and they will complete the NeuroQoL and Treatment Decision Question during T₃. If the T₃ visit occurs on or before June 30, 2021, the patient will be brought back in for a T₄ visit prior to September 1, 2021. Patients who have finished the study prior to protocol v. 10Jan2020 approval will be contacted via phone to obtain verbal consent, and will then be asked the Treatment Decision Question.

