their primary neurologist for consideration of restarting a MS DMT of their choice, or switching to an alternative DMT (if they were in the continuation arm). They will continue to be followed at all study time points with all procedures. This is a pragmatic trial, so individuals will continue to receive care from their primary neurologist (in many cases, this will be the Treating physician/PI as well). At all times, it will remain the choice of the patient and their physician to maintain or change the MS DMT. Any worsened neurological symptoms attributed to MS that are treated with systemic steroids, regardless of characterization above, will be counted as a Protocol defined relapse. In this context, it is imperative that patients contact the local PI of the study first and foremost, so that decisions about the use of steroids may be made by study personnel, and steroids used or not used after the determination of relapse status per the protocol.

An adverse event (AE) is the appearance or worsening of any undesirable sign, symptom, or condition occurring after starting the study even if the event is not considered to be related to study conditions or assignment. Study conditions or assignment includes assignment to continue or discontinue prior DMT. Medical conditions and diseases present before starting the study are only considered AEs if they worsen after starting the study. Abnormal laboratory values or test results constitute AEs only if they induce clinical signs or symptoms, are considered clinically significant, or require therapy.

The occurrence of AEs should be sought by nondirective questioning of the patient at each visit during the study. Adverse events also may be detected when they are volunteered by the patient during or between visits or through physical examination, laboratory test, or other assessments. All AEs must be recorded in the AEs eCRF with the following information:

1. the severity grade (mild, moderate, or severe)
2. its relationship to the study drug(s) (suspected/not suspected)
3. its duration (start and end dates or if continuing at final examination)
4. whether it constitutes a serious AE (SAE)

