Serious adverse events such as hospital admissions for > 24 hours, new significant medical diagnoses such as cancer (other than basal cell carcinoma), and MS relapse requiring corticosteroid use will be ascertained at each visit. SAEs should be reported to sponsor and entered into the electronic database within 24 hours of the event being reported to the study team. We will collect ongoing side effects of all DMTs, and non-serious adverse events in both groups, and report descriptive statistics and proportions on all adverse events. We will provide confidence intervals for the proportions and test them between treatments groups using the same type of methods used for the primary outcome.

E. Potential Scientific Problems:

Blinding of outcome measures is very important. As this is a pragmatic study, in which the research component is added on to the basic clinical visit, the Treating Physician/PI will have obtained a relapse history as part of that routine visit, yet is not blinded to the patient's medication assignment. The definition of relapse includes performance of the EDSS, and the separate EDSS Examining Clinician will be blinded to medication assignment, as well as to the relapse history, when doing the EDSS. While it might be preferential to have a relapse assessor separate from both the PI and the EDSS rater, this is impractical due to costs, the requirement to have a third clinician available at the visit, and the extra time of the visit. Thus, we will ask the PI to do a relapse assessment based on symptoms, but only make this information available to the EDSS Examining Clinician AFTER the EDSS is completed. The EDSS Examining Clinician will make the final assessment as to whether a Protocol defined relapse has occurred. While MRI readers and Examining Clinicians will be blinded to the patient's medication assignment, patients will not be blinded to medication assignment. Thus interpretation of the secondary Aims and Hypotheses as they relate to PROs will be potentially confounded by patient bias.

Significant efforts will be made to enroll only those patients who are truly willing to be randomized. If an excessive number of patients enter the study attempting to get into one or the other group assignment, they may be more likely to drop out if they do not receive the desired assignment, thus confounding data analysis.

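### Laboratory monitoring follows the individual DMT, so the between-arm test of all adverse events may partly reflect unequal looking, and the plan does not record how each event was found

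*Combined protocol and SAP*

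**What the plan says.** - **Section II, paragraph on the pragmatic design.** The patient or insurer pays for standard of care, including "all routine safety monitoring as would be obtained in a typical office setting for that individual medication". An earlier paragraph in Section II, on costs, gives laboratory studies as an example of the monitoring that comes with DMT use.
- **Section III.C, Table 1.** There is no laboratory row. Vitals, EDSS, relapse assessment and AE review are on one schedule for both arms, AEs are also asked about at the monthly calls, and all patients "undergo MRI scans of the brain at times T₀, T₁, T₂, and T₄".
- **Section III.D, detection of AEs.** "The occurrence of AEs should be sought by nondirective questioning of the patient at each visit during the study". Events may also come to light during "or between visits or through physical examination, laboratory test, or other assessments".
- **Section III.D, what counts.** "Abnormal laboratory values or test results constitute AEs only if they induce clinical signs or symptoms, are considered clinically significant, or require therapy". The three conditions are alternatives.
- **Section III.D, AE record.** Four items are captured: severity, relationship, duration and seriousness. How the event was found is not one of them.
- **Section III.D, analysis.** The team will "report descriptive statistics and proportions on all adverse events", give confidence intervals, and "test them between treatments groups using the same type of methods used for the primary outcome".
- **Section III.E.** The bias discussion covers assessor blinding, patient bias in PROs and dropout after an unwanted assignment. It does not mention AE ascertainment.

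**The concern.** A between-arm AE comparison is interpretable when both arms are looked at equally hard. Here one route of detection depends on the drug being taken, and therefore on the randomised assignment. Randomisation cannot balance that, and a larger sample would not remove it. If continuers have more blood tests, more incidental laboratory abnormalities will be recorded among them, even if such abnormalities are equally common in both arms.

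The tilt would favour discontinuation, which is the trial's hypothesis. AE proportions also feed the weighing of risks and benefits that Section III.G promises patients. Some laboratory AEs will be genuine harms of continuing. A single test on all AEs cannot separate those from unequal looking.

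**Working it through.** The plan gives no AE rate, AE sample size or AE power, so there is no figure to reproduce. The check is textual, followed by an illustration on assumed values.

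**Step 1. Is each route of detection equal in the two arms?**

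| Route | Source | Same in both arms? |
|---|---|---|
| Questioning at visits, monthly calls | III.D, Table 1 | Yes |
| Vitals, EDSS, scheduled brain MRI | Table 1 | Yes |
| SAEs asked about at each visit | III.D | Yes |
| Laboratory tests | II (standard of care, by drug); none in Table 1 | Not assured |

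Only the last row is in question. It bears on laboratory findings that cause no symptoms but are judged clinically significant or need therapy.

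**Step 2. Can the affected events be separated afterwards?** Not from the four AE items. Suspected relationship to study drug helps in part, but it is a judgement about cause and does not say how the event was found.

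**Step 3. How large could the effect be?** Inputs: n = 112 per arm (III.F, Sample Size Estimation). Section III.F expects exact methods for the primary outcome, so a two-sided Fisher test at 0.05 stands in for the AE test. Assumed: true risk r of a laboratory-detectable AE, equal in both arms; full detection in continuers; a fraction s detected in discontinuers. With a discontinuers and b continuers recorded as having such an AE,

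P = Σ Bin(a; 112, s·r) × Bin(b; 112, r), summed over a < b with Fisher p < 0.05.

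This is the chance of a significant result showing fewer AEs after discontinuation when there is no true difference:

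| r | s = 1 | 0.75 | 0.5 | 0.25 | 0.1 |
|---|---|---|---|---|---|
| 5% | 1.2% | 3.1% | 8.2% | 20.5% | 34.9% |
| 10% | 1.4% | 6.0% | 21.5% | 57.0% | 83.3% |
| 20% | 1.7% | 12.7% | 48.7% | 91.4% | 99.6% |

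The table treats laboratory-detected AEs as a category of their own.

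**Step 4. Dilution in an any-AE comparison.** Assume a true 30% with any AE in each arm, and that monitoring adds an AE in a further 10% of otherwise AE-free continuers: 0.30 + 0.10 × 0.70 = 0.37. Fisher rejects 16.5% of the time at 37% v 30%, against 3.6% at equality. If monitoring adds 5%, 0.30 + 0.05 × 0.70 = 0.335, and rejection is about 7%.

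**Step 5. The extreme case.** Suppose nothing is detected in discontinuers. For k v 0 events, the two-sided p is 2 × C(112, k) / C(224, k). This gives 0.12 for 4 v 0, 0.060 for 5 v 0, 0.029 for 6 v 0 and 0.0008 for 11 v 0. A rate of 5% corresponds to 0.05 × 112 = 5.6 patients, so even here the lower end straddles 0.05.

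**The case against.** The strongest objection is that the Section II sentence is about who pays. It does not say that laboratory tests stop on discontinuation, and the documents give no monitoring schedule for any DMT. That stands. A reader might infer that laboratory AEs are sought only in continuers and missed in discontinuers. The documents do not support this: ordinary care can include blood tests in either arm, findings from it can be reported at visits and calls, and Section III.D lets patients change DMT, which dilutes the contrast.

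A second objection is that the affected set is narrow and the consequence limited. AE comparison is not one of the three Specific Aims, and it has no margin, power statement or stopping rule. In a pragmatic trial, monitoring is arguably part of the strategy of continuing. This also stands, and it is a reason to keep the all-AE comparison. It does not remove the need to say what that comparison mixes together.

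A third is that confining the test to equally ascertained AEs would drop genuine laboratory harms of continuing and could tilt the result the other way. That is right, so the restricted comparison should supplement the planned one and not replace it.

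**Conclusion.** The point holds as a possible bias in one safety comparison. The plan fixes no common laboratory schedule, ties routine monitoring to the individual drug, admits symptom-free laboratory findings as AEs, and tests all AEs between arms without knowing how they were found. The likely direction is toward fewer AEs after discontinuation.

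The size cannot be derived from the documents. On the assumed values it runs from negligible (3.1% at r = 5%, s = 0.75) to large (57.0% at r = 10%, s = 0.25), and it is diluted when any AE is the outcome. All of this rests on the inference that monitoring is less frequent off a DMT. A reader might also infer that the trial's main safety conclusion is compromised. It is not: relapse, brain MRI, EDSS and the PROs follow the same schedule in both arms and do not depend on laboratory tests.

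**What to change.** 1. Add a how-detected field to the AE eCRF. For events already recorded, assign it from source records where available.
2. Keep the planned comparison of all AEs.
3. Beside it, add a between-arm comparison restricted to AEs found by routes common to both arms: visit questioning, monthly calls, scheduled assessments and SAEs.
4. Tabulate AEs found only through drug-related laboratory monitoring separately by arm, without a test. State that they mix genuine drug effects with unequal ascertainment.

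None of this changes monitoring, treatment or visits. The cost is one field and one extra table, plus some retrospective work. The current version provides for contacting patients who have already finished, so mode of detection will be incomplete for them. The restricted comparison also omits some genuine laboratory harms of continuing, so the two comparisons should be read together.

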 - i. **Neuro-QoL (quality of life) short form:** The Neuro-QoL Adult PRO short form measures are self-reported measures of overall quality of life and functioning relevant to and tested in patients with a variety of neurological conditions including MS since its introduction in 2011.⁷⁶ This measurement system, sponsored by the National Institute of Neurological Disorders and Stroke, is the newest PRO measurement system. It encompasses several domains including physical, emotional, social, and cognitive functions.³³ These scales are developed to assess health-related quality of life (HRQOL) and are developed to collect quality of life in patients with various Neurological disorders. This allows for future research where we can compare quality of life responses in this MS population as compared to other patients in the same age range with other neurological disorders. The Neuro-QoL short form represents a superior measurement system compared to the existing MS-specific PROs, as it is based on the newer item response theory (IRT) rather than the older classical test theory (CTT).⁷⁷ IRT has a number of advantages over CTT methods. Primarily, CTT models assume that measurement error is distributed normally and equally for all score levels.⁷⁸ In IRT, measures of precision are estimated separately for each score level or response pattern, controlling for the characteristics (e.g., difficulty) of the items in the scale. From these domains, the following item banks will be utilized: Physical Domains (Upper Extremity Function, Lower Extremity Function- Mobility), Symptom Domains (Fatigue, Sleep Disturbance), Mental Domains, Cognitive Domains (Applied Cognition- General Concerns, Applied Cognition- Executive Function, Communication), Emotional Domains (Anxiety, Depression, Positive Affect and Well-Being, Emotional-Behavioral Dyscontrol), Social Domains (Satisfaction with Social Roles and Activities, Ability to participate in social roles and activities). The Neuro-QoL short form scales consist of single scale item scales. Since we propose to use the static (i.e., each patient receives the same set of questions) short forms of each of these measures, most scales comprise 8 items and can be administered online or on paper, with a completion time of 1-2 minutes.

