This will be a randomized discontinuation trial (RDT).⁷¹ While RDTs have been done in cancer^{72,73} and rheumatoid arthritis patients,⁶⁶ this would be the first such study in MS. Patients will be randomized to either continue with their present MS DMT (control), or discontinue their present DMT (experimental), in a 1:1 fashion using the Interactive Voice Response System (IVRS) randomization system. A total of up to 265 patients will be consented and enter the trial. After allowing for up to 15% dropout rate, we aim for 225 (112 in each group) patients to complete the study. Patients enrolled after July 31, 2019 will not complete the full two years of assessments; study follow up will only continue until September 1, 2021. There will be no placebo, and no sham treatment. There will be no taper period. (Please see the statistics sections for power analyses).

At each site, extensive chart review will be used to identify eligible patients. Patients will be approached at their next standard of care clinical visit by their primary neurologist and/or a study coordinator about participating in the study. Either the patient's primary neurologist or the study PI will verify inclusion/exclusion criteria and ensure that all patient's questions are answered before consent is signed. Study information may be distributed in the community in order to recruit participants from other sources. Patients who do not receive their standard neurological care at the study site will be encouraged to transfer their neurological care to the study site for the duration of the study. If this is not possible, these subjects must agree to have standard of care MRIs done by their primary neurologist yearly throughout the study and have the results sent to the study site. MRIs at the 6-month time point must be conducted at the study site. All research visits will be conducted at the same time as SOC visits when possible, or as separate visits if not possible.

Please see Table 1 below for the schedule of study activities.

Table 1: Schedule of Research Assessments

MS Patients consented for the study	T ₀ (Baseline)	T ₁ (6 Months +/- 1 week)	T ₂ (12 Months +/- 1 week)	T ₃ (18 Months +/- 1 week)	T ₄ (24 Months +/- 1 week)***	Unscheduled Visit*	Phone follow-up (monthly +/- 1 week)
Informed Consent	X	-	-	-	-	-	
Inclusion/Exclusion	X	-	-	-	-	-	
Physical Exam/ MS Medical History	X	-	-	-	-	-	
Vitals	X	X	X	X	X	X	
Prior/Con Meds	X	X	X	X	X	X	X
Adverse Events	X	X	X	X	X	X	X

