c. Aim #3: Proposed Data Analysis: Descriptive statistics on patient demographics, PDSS, MSIS, performance and NeuroQOL short form scales, and all other PROs will be prepared for treatment group by occurrence of disease event, and qualitatively compared. Pre-Post change will be compared between treatment groups. Change scores will be used for continuous and metric outcomes, and the treatment groups will be compared with two sample T-tests, or Wilcoxon tests if necessary. Binary outcomes, such as dichotomized changes in EDSS and other scales, will be tested with chi-square and proportion tests, or exact analogs if necessary. MSIS will be divided into patients with greater or less than a change of 7.5 (considered a significant change). Correlations between continuous scales will be examined, and compared between treatment groups. Events will also be compared to non-events, and combinations of (event outcome) will be tested for differences, using similar methods, in the unlikely situation there are enough events to permit meaningful statistical analysis (≥ 10 samples for an analysis group). Multiple groups can be tested with ANOVA methods for continuous outcomes, and with chi-square tests and logistic regression for binary outcomes.

Sample Size Estimation: Our null hypothesis for AIM #1, inferiority of the discontinue group, is a disease event proportion of 0.02 for the continue group, and 0.10 for the discontinue group. Our alternate hypothesis for the power calculation, non-inferiority of the discontinue group, is a disease event rate of 0.02 for both the continue and discontinue groups. Our study population consists of stable patients, so we expect the disease event rate to be very small for the continue group, and possibly the discontinue group as well. For a target alpha level of 0.025, a sample size of 112 per treatment group (225 total), would achieve 95% power for the non-inferiority test. For a single treatment group with 112 samples, if the true proportion is 0.02, then the upper bound of an exact confidence intervals can be expected to be less than 0.11 more than 95% of the time. Anticipating a dropout rate of approximately 9-15%, we plan to attempt to recruit 132 patients per treatment group (265 total).

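### Neuro-QoL has one scheduled post-baseline assessment and no collection at withdrawal, so most early leavers would drop out of its open-label pre-post comparison

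*Combined protocol and SAP*

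**What the plan says.** Section III.C, Table 1, marks the Neuro-QoL short form at T0 and T4, with dashes at T1 and T2. The T3 cell carries the four-asterisk footnote. Under it, participants whose T3 comes after 30 June 2021 have no T4 "but will complete a NeuroQoL and Treatment Decision Question during T₃". For earlier T3 dates the three-asterisk footnote applies: "If T₃ is on or before June 30, 2021, participant should come in for an out of window T₄ visit before Sept. 1, 2021". Neuro-QoL is also marked in the Unscheduled Visit column. The table has no early-termination visit.

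MSIS-29, SymptoMScreen, PDDS (printed as PDSS in the table) and SDMT are marked at every visit.

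On the calendar, section III.C states "Patients enrolled after July 31, 2019 will not complete the full two years of assessments" and "study follow up will only continue until September 1, 2021". No enrolment closing date is given.

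On analysis, section III.F, Aim #3, says "Pre-Post change will be compared between treatment groups", using t-tests or Wilcoxon tests on change scores. It gives no rule for a missing post value and does not say whether an unscheduled value may serve as one.

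On retention, section III.E warns that if too many patients enter hoping for one particular arm, "they may be more likely to drop out if they do not receive the desired assignment".

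**The concern.** A change score needs a post value, and for Neuro-QoL the schedule offers one chance to obtain it. A participant who leaves at month 8 or month 20 will usually have only a baseline form and cannot enter the comparison. Patients know their assignment, and the protocol itself names dissatisfaction with assignment as a possible reason for leaving. If leavers in one arm differ in quality of life from leavers in the other, a comparison restricted to those who reach the final visit would be biased, with no later Neuro-QoL value to show it. Aim 3 asks whether quality of life is no worse after stopping treatment. Losing participants who did badly after stopping would make that arm look better than it was.

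The T3 substitute also presupposes that T3 happens before follow-up closes. For a sufficiently late enrolment it would not.

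**Working it through.** **1. The plan's own figures.** Inputs: 225 completers (112 per group), 15% dropout, 265 recruited (sections III.C and III.F); for Aims 2-3, alpha 0.05 with 0.38 SD for 80% power and 0.44 SD for 90% (section III.F).

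- Recruitment: 225 / 0.85 = 264.7, so 265; 112 / 0.85 = 131.8, so 132 per group. Both reproduce.
- Power of a two-sample t-test, 112 per group, two-sided alpha 0.05 (sidedness is not stated; two-sided assumed): 0.808 at 0.38 SD and 0.906 at 0.44 SD. Both reproduce.

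The 112 per group is counted after dropout, so planned early leaving takes nothing further from the stated power.

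**2. Participants without a scheduled post value.** 0.09 × 265 = 23.9, about 24; 0.15 × 265 = 39.8, about 40. This is an upper figure: a leaver with an unscheduled visit may have a value. Reaching the primary endpoint does not count as leaving, because section III.D keeps those participants in follow-up with all procedures.

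**3. Who falls under the T3 substitute.** 30 June 2021 minus 18 months = 30 December 2019. The substitute therefore applies to baselines after about that date. Participants enrolled from August to December 2019 still have a T4, in some cases early: 30 December 2019 to 1 September 2021 is about 20 months.

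**4. Where the substitute stops working.** 1 September 2021 minus 18 months = 1 March 2020, or about 8 March if T3 uses its one-week early window. For a later baseline neither T3 nor T4 occurs before follow-up ends, and no Neuro-QoL is scheduled. This protocol version is dated 10 January 2020, so the case was possible when it was written, but no document says enrolment continued that long.

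**5. Scale of the possible bias (illustration).** Let m be the fraction missing in each arm. Let D be the between-arm difference in how far completers' mean change departs from leavers' mean change. With equal m, the bias in the between-arm difference is m × D. The documents give no value for D. Setting it, as an assumption, to the plan's own 0.38 SD gives 0.09 × 0.38 = 0.034 SD to 0.15 × 0.38 = 0.057 SD. Unequal dropout between arms could make it larger; D near zero would make it negligible.

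**6. Loss beyond the 15% allowance (illustration).** Only this would cost power. A further 5% loss (106 per group) gives 0.79 at 0.38 SD; a further 20% (90 per group) gives 0.72. The documents give no basis for choosing a figure.

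**7. Burden.** Section III.A lists 13 Neuro-QoL item banks; at 1-2 minutes each, that is 13-26 minutes.

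**The case against.** The strongest reply is that the schedule is a reasonable trade-off. Visits are attached to routine care, the full set of forms is long, and MSIS-29, added because Neuro-QoL gives no overall quality-of-life score, is taken at every visit. Quality of life is therefore followed over time by another instrument. That stands, and it is why an extra T2 collection is optional.

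Several stronger readings are tempting, and the documents do not support them.

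- A reader might infer that every early leaver contributes nothing. Neuro-QoL is marked under Unscheduled Visit, and section III.C directs such a visit for any suspected relapse. The answer is only partial: that is the trigger the protocol describes, so these values would come mainly from people with new symptoms, and their use is unstated.
- A reader might infer that the protocol predicts differential dropout. Section III.E raises it conditionally and says efforts will be made to enrol only patients truly willing to be randomised; the inclusion criteria require asking about staying in either arm. No differential rate is given.
- A reader might infer lost power. Step 1 shows that the planned loss is already allowed for.
- A reader might infer that everyone enrolled after 31 July 2019 is affected. Step 3 shows otherwise.
- A reader might infer that the other outcomes would be analysed in a different population. The plan does not say that their interim values replace a missing final one. If they do not, the same leavers drop out of those comparisons too; the difference is that interim data exist for them.

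**Conclusion.** The point holds as a modest weakness in a secondary outcome. There is one scheduled post-baseline Neuro-QoL, no collection at withdrawal, and no rule for a missing post value. Up to about 24-40 of 265 participants would have no change score at the planned dropout, less any whose unscheduled-visit value is used. The consequence is possible bias, of unknown direction and size, in an unblinded comparison. The power statement is unaffected.

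The gap in the T3 substitute is conditional on enrolment after about 1 March 2020. The number affected cannot be computed from the documents and may be zero.

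The conclusion assumes dropout within the planned 9-15% and that leavers are not otherwise asked to complete the form. The improvement is worth making because it is cheap.

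**What to change.** Change Table 1 and the four-asterisk footnote so that Neuro-QoL is completed at the last study visit on or before 1 September 2021, whichever visit that is. The site can work this out from the baseline date. For a baseline after about 1 March 2020 and up to about 1 September 2020 it would be T2 (1 September 2021 minus 12 months = 1 September 2020).

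Add collection when a participant announces withdrawal. The short forms "can be administered online or on paper, with a completion time of 1-2 minutes", so no clinic visit is needed.

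In section III.F, Aim #3, name that last or withdrawal value as the post value, record the month it was taken, and state whether an unscheduled-visit value may stand in when neither exists.

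Collection at T2 for everyone is optional. It helps only participants not yet past month 12, and this version already refers to patients who may have finished the study.

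The cost is footnote and analysis wording, plus about 13-26 minutes of forms for those affected, with no added visits. The post values would be taken at differing months; the current rules already allow about 18 to 24, and withdrawal values would widen that range, which is why the month must be recorded and reported. Some people who withdraw will decline, so the gap shrinks but does not close.
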